CVS symptoms result in poorer visual performance, and even though they are transient, they occur frequently and cause considerable discomfort for sufferers. CVS lowers productivity (increased errors and more frequent breaks) and impinges on job satisfaction and quality of life [12]. Millions of individuals of all ages are at risk of CVS, and according to different studies, the prevalence of CVS ranges from 25% to 93%, depending on the cohort of the studied population, the definition and methodology employed to measure CVS [6]. These results indicate that a large proportion of the population may need treatment for CVS.

CVS affects all age groups, including older age groups (aged 65+), in which the use of technology is also rapidly growing [13]. However, the most affected population are younger users, who are more likely to simultaneously use two or more digital devices. For example, recent US data indicates that while adults aged 60 years and over prefer using laptops and desktops, younger adults are more likely to use smartphones too [5]. Since they use digital devices for work and social purposes (e.g. social media), they often multitask and switch between different devices.

The COVID-19 pandemic introduced homeworking and remote learning and further increased exposure to digital screens. Moreover, lockdowns increased unhealthy digital recreational activities, with people turning to television and social media for entertainment [18].

Management of Computer Vision Syndrome

CVS management includes correction of refractive error and/or presbyopia (long-sightedness caused by loss of elasticity of the lens of the eye, occurring typically in middle and old age; managed by prescribing a 'near add'), dry eye management, regular screen breaks, and eye exercises for vergence and accommodative problems (such as a lag in changing the focus from near to far distance) [6]. Some studies [6] have explored the role of blue light-filtering spectacle lenses with mixed results, indicating that blue light-filters may not alleviate symptoms of CVS. Given the high prevalence of CVS and near-universal use of digital devices, it is essential that eye care practitioners can provide advice and management options that are evidence based.

Aim

To evaluate the effectiveness and safety of the Super Enhanced Single Vision Lens 01 (SESL01) in reducing symptoms of Computer Vision Syndrome.

Key research questions

The key research questions of this study are:

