Is the SESL01 lens effective in

- I. Reducing the symptoms of the CVS compared with standard single vision lenses, assessed by the Computer Vision Syndrome Questionnaire (CVS-Q[®]) scores?
- III. Improving near visual performance when using digital devices, compared with standard single vision lenses, assessed by clinical measurement of accommodative facility using the standard ± 2.00 dioptre spherical lens flippers, measured as cycles per minute?

Trial Design

It is a double-blind two-arm parallel randomised control trial that aims to evaluate the effectiveness of SESL01 in CVS management. The study will mimic the routine optometric

practice, except that patients will be randomly allocated to the intervention or control groups. The patient's follow-up period is 14-week from the baseline.

Methods

Study setting

The study will be conducted at the University of Central Lancashire on the Preston campus in the UK.

Participants eligibility criteria

Inclusion criteria:

- I. Able to provide informed consent
- II. 21-45 years of age
- III. Adults diagnosed with CVS: CSV-Q score ≥ 6
- IV. Participants WITH AND WITHOUT refractive error are acceptable BUT none should have previously worn a "near add" correction (e.g. no previous bifocal/varifocal/enhanced single vision lens [ESL] wear)
- V. Range of refractive errors should be no more than +4.00 to -6.00 dioptic spherical power (DS) and +2.00 dioptic cylindrical power (DC)
- VI. Must use digital devices for work and/or leisure for at least 1 hour per day (this includes smartphones, tablets, and laptops but EXCLUDES PC-only users)
- VII. Patients MUST have visual symptoms associated with digital device use, e.g. one or more of the following symptoms:
 - a. Tired eyes
 - b. Eye strain
 - c. Blurred vision
 - d. Frontal headaches
 - e. Difficulties keeping clear vision when changing focus from near to distance
 - f. Difficulties keeping clear vision when changing focus from one device to another

Exclusion Criteria:

- I. Lack of capacity to provide informed consent.
- II. Amblyopia
- III. Pregnancy
- IV. Diagnosed dry eye disease

- V. If a patient develops dry eye symptoms or is diagnosed at follow-up appointments, treatment will be started and assessed in two weeks.
- VI. On anti-depressants (or other medication that can affect accommodation, such as reduced focusing power)
- VII. Any diagnosed ocular pathology (such as glaucoma, corneal dystrophies, lid disorders, and retinal pathologies)

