Wilkins Rate of Reading		x		x	x	x
Accommodative Facility in cycles per minute (with spherical lens flippers and Zeiss own brand app)		x		x	x	x
Thomson Clinical Eye Tracking (with blink rate)		x		x	x	x

Near Visual Performance (NVP) includes all the assessments (variables) listed after the CVS-Q

Figure 1 CONSORT flow diagram

CVS-Q: Computer Vision Syndrome Questionnaire; NVP: Near Visual Performance

Criteria for discontinuing or modifying allocated interventions

- i. Participant withdraws consent
- ii. The trial is discontinued
- iii. Participant requires hospitalisation or out-patient ocular surgical treatment

The reasons for discontinuation will be documented. Participants will be invited to participate in an outcome-related assessment to determine the effectiveness of the intervention. Participants will be asked to return the spectacles provided for the study.

Strategies for monitoring and improving protocol adherence

There are some measures that clinicians could adopt to improve patient adherence to the research protocol, such as telephone calls, text reminders, and social support to educate patients on using their spectacles. In addition, clinicians will have to create a welcoming, non-judgmental, and accepting environment; educate patients about their role as research participants; establish a routine while maintaining flexibility; provide incentives for participation, such as Amazon vouchers, parking spaces, and video consultations.

Research instrument

The CVS will be assessed using the CVS Questionnaire (CVS-Q) developed by Seguí et al.' [21]. The CVS-Q has questions on 16 ocular and visual related symptoms which will be presented to the patients. These symptoms are burning, itching, feeling of a foreign body in the eye, tearing, excessive blinking, eye redness, eye pain, heavy eyelids, dryness, blurred vision, double vision, difficulty in focusing on near objects, increased sensitivity to light, coloured halos around objects, feeling that sight is worsening, and headache. The frequency of these symptoms is defined based on how often they occur: sometimes or occasionally, once per week, always or often if they occur two to three times per week or every day [7]. The intensity of the symptoms is scored as never=0, mild to moderate=1, severe=2. To measure the frequency of the symptoms, patients will be asked to choose the following options for each of them: never=0, sometimes or occasionally=1, always or often=2.

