The following formula will be used to calculate the total score

$$\text{Score} = \sum_{i=1}^{16} (\text{frequency of symptom occurrence})_i \times (\text{intensity of symptom})_i$$

Seguí et al. [17] suggested that a good balance between sensitivity and specificity is represented by a cut-off value of 6 for the total CVS-Q score. Therefore, patients with a CVS-Q total score ≥ 6 are suffering from CVS and will be included in the study. In the absence of a universal consensus on CVS severity grading, Alhasan et al. [24] adopted the following criteria: participants with a total score of 6-12 were deemed to have mild CVS, those with a score of 13-19 moderate, and those with a score ≥ 20 were considered to have severe CVS.

Outcomes

Primary outcome

The primary outcome measure is the effectiveness of the SESL01 in reducing the CVS compared with standard single vision lenses, assessed using the CVS-Q® scores at week 14.

Secondary outcome

The secondary outcome is the effectiveness of SESL01 compared with standard single vision lenses in improving the near visual performance when using digital devices assessed by clinical measurement of accommodative facility in cycles per minute using spherical lens flippers as well as optometric tests such as near LogMAR visual acuity, amplitude of accommodation, near point of convergence and rate of reading.

In addition to performance of the lens in terms of reducing CVS and improving near vision function, the study will consider the safety of the lens before it can be prescribed safely to the wider population.

Sample size

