The primary outcome measure (CVS-Q score) will be assessed at week 14 using an unpaired analysis. The analysis will be performed without adjustments; then, it will be adjusted using the baseline CVS-Q scores, age, and gender and the CVS-Q at 6 and 10 weeks using generalized estimating equations (GEE), which is a semiparametric technique useful for repeated measures that work for dichotomous and continuous data, as in our case.

Secondary outcomes

The secondary outcome measure, the improvement of the near visual performance when using digital devices using SESL01 compared with standard single vision lenses will be assessed using the clinical measurement of accommodative facility in cycles per minute using spherical lens flippers at week 14 as well as optometric tests such as near LogMAR visual acuity, amplitude of accommodation, near point of convergence and rate of reading.

Secondary analysis

The secondary analyses will be performed looking at

- the percentage of CVS-Q score <6 (no symptoms) versus CVS-Q score ≥6 (symptoms) in each group at 14 weeks. The results will be presented using descriptive statistics at each time point, and the differences will be assessed using Pearson's Chi-square test or Fisher's exact test and odds ratio (OR).

- The percentage of participants in each group with a total CVS-Q score <6, 6-12, 13-19, and ≥ 20 at week 14. The results will be presented using descriptive statistics at each time point, and the differences will be assessed using the Mann Whitney U test.

A P-value of ≤ 0.05 will be considered statistically significant and presented with 95% confidence interval where appropriate. The statistical analysis will be performed using SPSS (IBM Corp. Released 2021. IBM SPSS Statistics for Windows, Version 28.0. Armonk, NY: IBM Corp).

Data monitoring

This trial was designed to minimise the risk, as demonstrated in a previous trial [20]. Therefore, no formal committee has been organised, and no interim analysis of the impact of the intervention has been planned. The study is a monocentric study conducted at the UCLan campus in Preston.

Risk and safety issues

During this study, there will be no risks for patients. Patients wearing the SESL01 lenses will be at no greater risk than those receiving the usual ones. Clinicians will not dispense or administer any medications based on the CVS-Q score. In addition, clinicians will not be involved in the interpretation of diagnostic tests or their results.

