Covid safety protocols:

Participants will be required to wear a face covering throughout the examinations while in the eye clinic (unless they are exempt). Before the visit, participants will be asked to complete a COVID-19 Research Participant Pre-Visit Check Form, which will be used to prevent the spread of COVID-19 and to reduce the potential risk of exposure. If participants are displaying any COVID symptoms, their data collection appointment will be rescheduled by a week. If participants display any COVID-19 symptoms during, or after the visit, the PI should be informed, so that the necessary steps can be taken according to relevant government guidelines.

The clinicians in the study will be wearing personal protective equipment, and all equipment and room surfaces will be cleaned between participant visits.

Harm

We do not expect adverse events or other unintended effects. All information regarding the trial will be included in the clinicians' and patients' information sheets.

[figure not shown]
Spectacle dispensing and prescribing can cause 'non-tolerance'. Non-tolerance is when a participant is not satisfied with their spectacles, which may be due to the lack of clarity of vision or discomfort caused by the frames [20].

Cases of non-tolerance [15] can be split into:

- I. Dispensing: This is where the fitting of the frame or the dispensing measurements were not correct for the participant.
- II. Prescription: The participant is not able to adapt to the prescription or there was a data entry error, and the incorrect prescription was ordered.

Cases of non-tolerance are small; research shows that cases in general optometric practice range between 1% to 3% [16]. The implication of this data for our study is that approximately 7 participants may report dissatisfaction with their spectacles. A procedure to handle cases of non-tolerance is summarised in Figure 2.

Figure 2 Process for handling non-tolerance

Process for dealing with a case of spectacle non-tolerance.

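### Safety is a stated aim tied to wider prescribing, but the visible plan names no safety outcome, schedules no adverse-event or non-tolerance enquiry, and plans no by-arm safety summary

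*Combined protocol and SAP*

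**What the plan says.** The Aim section reads "To evaluate the effectiveness and safety of the Super Enhanced Single Vision Lens 01", and the summary table at the front of the document also includes safety. The Secondary outcome section adds that "the study will consider the safety of the lens before it can be prescribed safely to the wider population". No variable, time point or analysis follows that sentence.

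Several other provisions bear on safety:

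- **Harm** divides spectacle non-tolerance into a dispensing class and a prescription class, expects about 7 participants to report dissatisfaction, and refers to Figure 2 for handling. Non-tolerance that remains after retest and re-dispense goes to the sponsor as an adverse effect within 3 working days, and the sponsor informs the regulator.
- **Criteria for discontinuing or modifying allocated interventions**: "The reasons for discontinuation will be documented".
- **Exclusion Criteria, item V** foresees dry eye during follow-up: "If a patient develops dry eye symptoms or is diagnosed at follow-up appointments", followed by a management statement.
- **Research instrument**: "The CVS-Q has questions on 16 ocular and visual related symptoms which will be presented to the patients". Table 1 repeats the questionnaire and acuity at W6, W10 and W14.
- **Data monitoring** states that there is no formal committee and no interim analysis.

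**The concern.** A trial that lists safety in its aim, and links it to wider prescribing, should be able to report what happened to wearers in each arm. On the visible text it can report CVS-Q scores and acuity by arm. It has no planned answer to how many participants in each arm had an adverse event or could not tolerate their spectacles.

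This is more than a missing table. A table can be added at the analysis stage, but answers to a question that was never asked cannot be recovered then. If complaints reach the record unevenly, a by-arm count put together afterwards may reflect who spoke up rather than what the lenses did. With no committee and no interim look, an end-of-trial summary would be the only comparative view of safety. What is at stake is the safety conclusion alone.

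**Working it through.** **1. From the aim to the analysis.**

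| Part of the plan | Safety content in the visible text |
|---|---|
| Aim | Safety named alongside effectiveness |
| Primary outcome | CVS-Q at week 14, as effectiveness |
| Secondary outcome | Near visual performance, as effectiveness; then one general sentence on safety |
| Table 1 | No adverse-event or non-tolerance row; slit lamp (with tear break-up time), fundus, OCT, intra-ocular pressure and visual fields at W0 only |
| Data collection | Questionnaires at baseline and every 4 weeks; no adverse-event form named |
| Statistical methods | CVS-Q, near visual performance and CVS-Q categories; no safety variable or by-arm safety table |

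**2. Whether existing data fill the gap.** The CVS-Q is analysed as a total and as bands of the total, so one item that worsens can be offset by others that improve. Near acuity is compared between arms, but as an effectiveness outcome. Discontinuation reasons are recorded without a stated summary. Only non-tolerance that persists after retest and re-dispense is labelled an adverse effect; cases that resolve have no stated place in the results.

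**3. The plan's own figure.** Inputs: 300 participants, 150 per arm (Sample size); non-tolerance 1% to 3%, about 7 expected (Harm).

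- 300 × 0.01 = 3; 300 × 0.02 = 6; 300 × 0.03 = 9.
- 7 / 300 = 2.3%, inside the range; 7 / 2 = 3.5 per arm.

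The stated 7 is consistent with the plan's range, and the plan itself expects some cases.

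**4. How precise a by-arm count would be.** The plan gives no rate by arm, so near-even splits are assumed. The interval is Newcombe's, built from the Wilson limits (l, u) of each arm: lower = d − √[(p1 − l1)² + (u2 − p2)²], upper = d + √[(u1 − p1)² + (p2 − l2)²].

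For 4 v 3 at 150 per arm, in percentage points:

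- p1 = 4/150 = 2.67, Wilson limits 1.04 to 6.66; p2 = 3/150 = 2.00, Wilson limits 0.68 to 5.72; d = 0.67.
- Lower = 0.67 − √(1.63² + 3.72²) = 0.67 − 4.06 = −3.4.
- Upper = 0.67 + √(3.99² + 1.32²) = 0.67 + 4.20 = +4.9.

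The same method gives −2.5 to +4.1 for 2 v 1 (3 cases in all) and −3.8 to +5.2 for 5 v 4 (9 cases).

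**5. An empty arm.** P(no cases in 150) = (1 − p)^150: 0.99^150 = 22% at 1%, 3% at 7/300, and 1% at 3%. At the low end of the plan's range, an arm with no cases is plausible. The exact two-sided 95% upper limit for 0/150 is 1 − 0.025^(1/150) = 2.4%, so an empty arm would not show that non-tolerance is absent.

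**The case against.** The best reply is that the plan is not silent on harm. It has a non-tolerance process, a reporting deadline, a route to the regulator, documented reasons for discontinuation, and blinded CVS-Q and acuity assessments in both arms at three visits. Those capture the main visual complaints. The product is a spectacle lens, and a safety table could only be descriptive. All of that stands. It keeps the point modest, but it does not supply a safety outcome, a scheduled enquiry or a by-arm count.

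Four stronger readings are tempting and are not supported:

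- **That the trial has no safety provision.** The Harm section alone rules this out.
- **That complaints outside the questionnaire are recorded only when a participant volunteers them.** No section says so. Figures 1 and 2 are not shown and may log withdrawals or earlier cases. What can be said is that no scheduled enquiry is visible.
- **That dry eye at follow-up is already collected and needs only tabulating.** Item V is a management statement. Slit lamp and tear break-up time are scheduled at W0 only; the repeated measure is the CVS-Q dryness item.
- **That the plan contradicts itself on risk.** "During this study, there will be no risks for patients" and "We do not expect adverse events or other unintended effects" sit awkwardly beside about 7 expected reports of dissatisfaction. But the sentence after the first statement is comparative with usual lenses, non-tolerance is described as a feature of spectacle prescribing in general, and only persistent cases are called adverse effects. This is a matter of wording.

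It could also be argued that every non-tolerance case should be sorted by cause, because the prescription class joins two different things: "The participant is not able to adapt to the prescription or there was a data entry error, and the incorrect prescription was ordered". Separating them would be informative, but making it compulsory could require a check of lenses against orders and someone outside the blinded team. The stated gap can be closed without that.

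**Conclusion.** The point holds on the visible text: safety is an aim, yet there is no named safety outcome, no scheduled adverse-event or non-tolerance enquiry, and no by-arm safety summary. It should be put right before follow-up data are collected, because the enquiry cannot be added in retrospect. It does not touch the primary or secondary efficacy analyses.

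The numbers are small: 3 to 9 expected cases, about 7 on the plan's own figure. An interval of roughly −3.4 to +4.9 points for a 4 v 3 split supports a descriptive summary and no more. This rests on an assumed near-even split, on all 150 per arm collecting spectacles, and on a general-practice rate applying to this trial. Confidence is medium, because Figures 1 and 2 are unseen and may record some cases.

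**What to change.** Leave non-tolerance handling, and reporting to the sponsor and regulator, unchanged.

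1. **Table 1.** Add one row at W6, W10 and W14. The blinded clinician asks, in the same words in both arms, about adverse events and spectacle non-tolerance since the last visit. Record every report, whether resolved or persistent.
2. **Statistical methods, new safety table.** Among participants who collected spectacles, give by arm the number and percentage with any adverse event and with any non-tolerance, using the dispensing and prescription classes in Harm. Add a 95% CI for the difference, label the table descriptive, and carry out no test. Separating failure to adapt from data-entry error is optional, where the handling process already shows which it was.
3. **Statistical methods, existing data.** Tabulate by arm the CVS-Q items worse than baseline, acuity change from baseline, and documented discontinuation reasons. Include dry eye only as reported through the new enquiry.

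The cost is a short case report form item at three visits that already take place, and two descriptive tables, one of them from data already collected. The drawback is that more minor complaints will be recorded, including frame-fit problems unrelated to the lens.

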Seguí-Crespo et al. [20] and Alhasan et al. [24] suggested that the CVS-Q score is not normally distributed. Alghamdi and Alrasheed [23] and Sanchez Brau et al. [25] summarised their findings using means and a wide range of standard. Therefore, in our study it was decided to conduct the power calculation using a standard deviation of 3.5, which is within the 1.8-6 range. We also assumed an initial normal distribution in the arms with expected means of 8 in the control and 6 in experimental groups. We then estimated the power for different sample sizes by simulation, truncating the values generated to select those at least 6. The result was that a sample size of 150 per group would give us a power of 80% to detect the clinically important difference of 2, even allowing for a dropout of 10%. Therefore, with a 1:1 allocation and sample size of 300 patients (150 in the intervention group [IG] and 150 in the control group [CG]), we expect there to be sufficient power to detect this effect size.

Recruitment

Recruitment will be focussed mainly on students and staff within the University of Central Lancashire.

Student recruitment: Announcements on the virtual learning platform (the Blackboard) will be used along with posters around the campus with the details of the study. Project invites can be sent out via Social Media accounts and student email addresses. The university has a large portion of mature students, so recruiting patients within the required age range will be possible.

Staff recruitment: Emails, announcements on internal comms, social media accounts, work email addresses, and posters will be used to encourage colleagues to participate.

Recruitment will start as soon as University ethics and NHS REC approval have been granted and the sponsor has opened the study site.

The recruitment strategy will increase potential participants' awareness of the health problem being studied, its potential impact on their health, and engagement in the learning and training of healthcare professionals.

Clinician-patient ratio

For eye test and clinical measurements, the ratio of participants to clinicians is 150:1 but each interaction/data collection appointment will be on a 1:1 basis.

For spectacle frame selection and measurements, the ratio is 300:1; however, each interaction will be on a 1:1 basis.

Randomisation, sequence generation, allocation, and blinding

Randomisation

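### The stated 80% power does not belong to a difference of 2: truncating the simulated outcome at 6 shrinks the difference to about 0.86, and the untruncated inputs give over 99% power

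*Combined protocol and SAP*

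**What the plan says.** The Sample size section sets out to "conduct the power calculation using a standard deviation of 3.5, which is within the 1.8-6 range". On the arms it says: "We also assumed an initial normal distribution in the arms with expected means of 8 in the control and 6 in experimental groups". Power was then estimated "by simulation, truncating the values generated to select those at least 6". The reported result is that "a sample size of 150 per group would give us a power of 80% to detect the clinically important difference of 2", with 10% dropout allowed for and 1:1 allocation of 300 patients. Neither the test nor the sidedness used in the simulation is given.

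Three other places bear on this:

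- The inclusion criteria and the Research instrument section make a CVS-Q score of at least 6 a condition of entry.
- The Primary outcome sections compare the arms on the CVS-Q score at week 14, using an unpaired analysis.
- The Secondary analysis section compares "the percentage of CVS-Q score <6 (no symptoms) versus CVS-Q score ≥6 (symptoms) in each group at 14 weeks", and a further analysis there uses scores below 6 as the lowest of four severity categories.

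**The concern.** A score of at least 6 is needed to enter the trial, so it limits what patients can score before treatment. It does not limit what they score at week 14. The simulation nevertheless applied it to values drawn from the two arm distributions that differ by treatment, which are the outcome being compared.

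This has two consequences. First, removing everything below 6 takes more from the arm centred on 6 than from the arm centred on 8, so the simulated arms no longer differ by 2. Second, the simulated trial has nobody below 6 at week 14, although two planned secondary analyses depend on there being such patients.

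The paragraph is what an ethics committee or a reader uses to judge why 300 people are needed. It tells them that a 2-point effect requires this number, and that the chance of missing such an effect is one in five. Neither statement follows from the inputs given.

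**Working it through.** **Inputs.** From Sample size: means 8 (control) and 6 (SESL01), SD 3.5 (quoted range 1.8 to 6), 150 per arm, 10% dropout, truncation at 6. Evaluable: 150 × 0.9 = 135 per arm. From Secondary analysis: "A P-value of ≤ 0.05 will be considered statistically significant". Two-sided testing is assumed, because the plan does not say.

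**1. What truncation does to the difference.** For a normal with mean μ and SD σ cut below at 6, let a = (6 − μ)/σ and λ = φ(a)/(1 − Φ(a)). The truncated mean is μ + σλ and the truncated SD is σ√(1 + aλ − λ²).

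- Control: a = −0.571; λ = 0.3388/0.7161 = 0.473; mean 8 + 3.5 × 0.473 = 9.66; SD 2.49.
- SESL01: a = 0; λ = 0.3989/0.5 = 0.798; mean 6 + 3.5 × 0.798 = 8.79; SD 2.11.
- Difference: 0.86 from unrounded values, not 2.

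Before truncation, 1 − 0.716 = 28% of controls and 50% of SESL01 patients fall below 6. After it, none do.

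**2. Attempt to reproduce the 80%.** For the truncated model with 135 per arm, SE = √[(2.49² + 2.11²)/135] = 0.281. Then 0.863/0.281 = 3.07, and Φ(3.07 − 1.96) = 87%. Simulation (5,000 to 6,000 trials per setting) covered the other readings of the text:

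| Handling of values below 6 (SD 3.5) | Mean difference | Power at 135 per arm: t-test | Mann-Whitney |
|---|---|---|---|
| Redrawn until at least 6 | 0.86 | 87% | 83–84% |
| Redrawn, then rounded to integers | 0.86 | 86% | 82.5% |
| Discarded, leaving about 97 and 67 | 0.86 | 66% | 61% |
| Set to 6 | 1.22 | 99% | 99% |
| Not truncated | 2 | 99.7% | 99.5–99.6% |

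At the full 150 per arm, the redrawn version gives about 90% (t-test) or 86–88% (Mann-Whitney). None of these variants at SD 3.5 comes within 2 points of 80%. The nearest is the redrawn version with a Mann-Whitney test, and its difference is 0.86.

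**3. Power for the stated difference of 2.** SE = 3.5 × √(2/135) = 0.426; 2/0.426 = 4.69; Φ(4.69 − 1.96) = 99.7%. The noncentral t gives the same figure, and 99.9% at 150 per arm.

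**4. Sample size for 80% power at a difference of 2.** n = 2 × 3.5² × (1.960 + 0.842)²/2² = 48.1, so 49 per arm by the normal approximation and 50 by the noncentral t. With 10% dropout, 50/0.9 gives 56 per arm, or 112 in total.

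**5. What 135 per arm can detect.** At SD 3.5, the difference with 80% power is (1.960 + 0.842) × 0.426 = 1.19, or 1.20 by the noncentral t. At SD 6, power for 2 points is 77.9% (noncentral t) or 78.2% (normal approximation); at 150 per arm it is about 82%.

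**The case against.** The best defence is that 80% was meant as a floor. The section says that scores are not normally distributed, so a rank test is plausible. The truncated model with a Mann-Whitney test at 135 per arm gives 82.5–84%, and 150 is a round number chosen from several sizes tried. On that reading the power is roughly reproduced and only its label is wrong. This may well be how the figure arose, and without the test, the sidedness or the code it cannot be settled. It does not rescue the statement, because the power would still be for 0.86 and the plan says it is for 2.

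A second defence is that the error is conservative. That stands at SD 3.5: the trial has more power for 2 points than it claims, and no planned analysis is invalidated. It does not stand across the whole quoted SD range, since power falls just under 80% at SD 6.

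Third, the untruncated normal is itself only a model. It puts 4.3% of SESL01 scores below zero, which the CVS-Q cannot produce, so the 50% and 28% below 6 are model outputs and not forecasts. This is fair. The direction is robust, though: applying the cut-off to baseline only, with a floor at zero and assumed baseline to week-14 correlations of 0.3 to 0.7, still gave power above 99%.

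Finally, any trial can reach significance at an observed difference below its target, so that possibility is not counted here as part of the error.

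**Conclusion.** The concern holds. The simulation as described compares arms that differ by about 0.86, while the plan presents its power as that for a difference of 2. On the plan's own untruncated inputs, the power for 2 points is 99.7% with 135 evaluable per arm, and the planned 150 per arm is about 2.7 times the 56 needed for 80% power (150/56).

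These figures assume a two-sided 5% test, 10% dropout and normal scores with SD 3.5. The exact origin of the 80% cannot be traced, but the mismatch between the stated power and the stated difference does not depend on it. The fault lies in the justification of the sample size. The trial is not underpowered for 2 points unless the SD is close to 6.

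**What to change.** Rerun the calculation with the cut-off of 6 applied to baseline scores only, leave the week-14 scores free to fall below it, and name the test and the sidedness. Then restate the result. For example: 300 patients with 10% dropout give over 99% power for a 2-point difference at week 14 if the SD is 3.5, about 78% if the SD is 6, and 80% power for 1.2 points at SD 3.5 (two-sided 5%, t-test). If the sponsor wants 300 to rest on an 80% figure, the paragraph should justify it by a larger SD or a smaller target difference and say so.

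As a separate, optional addition, the plan could say that the 95% confidence interval will be read against the 2-point important difference as well as against zero.

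The cost is a rewrite of one paragraph. No patients, visits or analyses are added, and the sample can stay at 300.
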